As-treated time to the first occurrence of individual components of the composite endpoint:

- All-cause death
- Liver transplant
- Hepatic decompensation requiring hospitalization assessed through claims or registry CRF and defined as first occurrence of:
 - Variceal bleed
 - Ascites (including hepatic hydrothorax and spontaneous bacterial peritonitis)
 - Hepatic encephalopathy

Exposure Variable:

The exposure variable is the use of OCA initiated at the index date.

Covariates:

The following covariates/control variables will be assessed **in the pre-index period**, utilizing the value closest to the index date:

- Age at index date
- Sex
- Most recent liver biochemistry levels (TB, ALP, ALT, AST)
- Most recent platelet counts
- Time (in months) since UDCA failure
- Clinical evidence of portal hypertension (platelets <150,000 and/or non-bleeding varices)
- Cirrhosis
- Most recent Charlson Comorbidity Index Score
- Insurance type at index date (Komodo Health only)

Statistical Methods:

Analysis Populations

The statistical analysis of the HEROES PBC studies will follow a nested randomized trial emulation approach (Hernán 2008, Danaei 2013) using a treatment decision design to identify index events (Brookhart 2015). Due to the lack of randomization, non-randomized observational studies will instead be conducted, with the goal of mimicking the hypothetical randomized trial as closely as possible. All patients will be evaluated over time from the start of the study period to identify evidence of inadequate treatment response to UDCA. Each date of inadequate response identified in the data will be considered a treatment decision point, and that date will be considered an index date, with a corresponding record created in the analytic data for that patient index. Each patient can contribute multiple index dates and thus patient indices, corresponding to each date they have a treatment decision point, and therefore each patient may contribute person-time to multiple patient index records.

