7.1.1. Definition of UDCA Failure

UDCA failure includes both inadequate response to UDCA, and intolerance to UDCA. Inadequate UDCA response is defined as:

- At least 1 measure of ALP and/or TB >ULN; and
- \geq 270 days of UDCA treatment prior to ALP and/or TB elevation

UDCA intolerance is defined as:

• A maximum of 90 days of UDCA use with ALP>ULN and/or TB >ULN.

The first date of prescription of OCA after inadequate UDCA response (ALP>upper limit of normal [ULN] and/or total bilirubin [TB]>ULN after >270 days of treatment) or UDCA intolerance (discontinued UDCA after <90 days despite ALP>ULN and/or TB>ULN) will be defined as the index date for OCA-treated PBC patients. The dates of evidence of inadequate UDCA response or UDCA intolerance during which OCA is not utilized will be used as index dates for the non–OCA-treated comparator group.

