7.3. Exclusion Criteria

A patient who meets **any** of the following criteria for a given index date is not eligible for inclusion:

- History or presence of other concomitant liver diseases before the index date (inclusive), including:
 - Acute or chronic hepatitis C virus infection
 - Acute or chronic hepatitis B infection

- Primary sclerosing cholangitis
- Active alcoholic liver disease
- Hepatocellular carcinoma
- Hepatorenal syndrome
- Hepatopulmonary syndrome
- Portopulmonary syndrome
- NASH
- History of non-skin malignancy or melanoma before the index date (inclusive)
- History of HIV before the index date (inclusive)
- Medical conditions that may cause non-hepatic increases in ALP:
 - Paget's disease during the 12-month period before the index date (inclusive)
 - Fractures within 3 months before the index date (inclusive)
- Patients with laboratory values indicative of hepatic decompensation or significant hepatobiliary injury before the index date (inclusive):
 - TB >3 mg/dL
 - ALP >10x ULN
 - ALT and/or AST >10x ULN
- History of liver transplant before the index date (inclusive)
- Evidence of OCA, fenofibrate, or bezafibrate use before the index date (inclusive)
- History or presence of any of the following hepatic decompensating events before the index date (inclusive):
 - Variceal bleeding
 - Ascites
 - Hepatic hydrothorax
 - Spontaneous bacterial peritonitis
 - Hepatic encephalopathy

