7.4. Group Assignments

Treatment group (OCA-treated): ≥ 1 prescription or medical claim for OCA at or after UDCA failure date. The first date will be the one index date.

Control Group (Non-OCA-treated but eligible for OCA): Each date corresponding to evidence of a patient meeting the definition of UDCA inadequate response or intolerance in which the patient meets the inclusion and exclusion criteria and does not initiate OCA will be an

index date for the non–OCA-treated patient group. Patients may contribute indices to this group before they initiate OCA, but not after OCA index.

A thorough description of methodology underlying group assignment can be found in Section 10.1.1.

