8.3. Exposure Variable

The exposure variable initiates at the OCA index date. In the Komodo database, OCA exposure will be assessed as date of first filled prescription and quantified as days supply. Discontinuation will be assessed by a gap of >90 days after previous days supply. Treatment exposure will be continued for 90 days after last days supply, after which the OCA-treated patient will be censored. In the Global PBC database, OCA exposure will be from the first physician reported utilization date to discontinuation date, plus 90 days. In this study, exposure can range from 1 to 67 months.

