10. STATISTICAL METHODS

10.1. Analysis Populations and Blinding

10.1.1. Analysis Populations

The statistical analysis of the HEROES PBC studies will follow a nested randomized trial emulation approach (Hernán 2008, Danaei 2013) using a treatment decision design to identify index events (Brookhart 2015). The goal of the study design is to emulate a sequence of hypothetical randomized trials. In each hypothetical trial, patients meeting the inclusion and exclusion criteria who are making the decision whether to initiate OCA-based treatment are

randomized to either continue their existing PBC treatment or switch to an OCA-based treatment. Each randomized patient is then followed until the earliest of the end of follow-up or the time of the study endpoint (death, liver transplant, or hospitalization for hepatic decompensation). Standard survival analysis methods (eg, a Kaplan-Meier estimator of the cumulative incidence function or a Cox proportional hazards model to estimate the hazard ratio) will then be used to estimate the effect of OCA on the study endpoint.

Due to the lack of randomization, non-randomized observational studies will instead be conducted, with the goal of mimicking the hypothetical randomized trial as closely as possible. All patients will be evaluated over time from the start of the study period to identify evidence of inadequate treatment response to UDCA. Each date of inadequate response identified in the data will be considered a treatment decision point, and that date will be considered an index date, with a corresponding record being created in the analytic data for that patient index. Each patient can contribute multiple index dates, and thus patient indices, corresponding to each date they have a treatment decision point, and therefore each patient may contribute person-time to multiple patient index records.

At each treatment decision point, the inclusion and exclusion criteria will be assessed (see Sections 7.2 and 7.3). For patient indices meeting the study criteria, all baseline covariates and treatment variables will be determined. Person-time corresponding to each patient index will be computed relative to the date of the index event. Notably, because prior treatment with OCA is an exclusion criterion, a patient may contribute at most one OCA-treated patient index event, though they can contribute multiple non–OCA-treated patient index events.

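### Read literally, the OCA part of the prior-treatment exclusion makes every OCA-treated index ineligible; this is a drafting contradiction with low practical risk

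*Combined protocol and SAP*

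**What the plan says.** Among the exclusions in Section 7.3 is "Evidence of OCA, fenofibrate, or bezafibrate use before the index date (inclusive"). The synopsis has the same bullet in the same words. The lead-in to Section 7.3 says that a patient who meets any of the listed "criteria for a given index date is not eligible for inclusion". No exemption is given for the OCA group.

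On when the criteria apply, Section 10.1.1 says: "At each treatment decision point, the inclusion and exclusion criteria will be assessed".

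Four places fix the OCA index date:

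- Section 7.1.1: the first OCA prescription after UDCA failure "will be defined as the index date for OCA-treated PBC patients".
- Section 7.4: the treatment group needs at least one OCA prescription or medical claim at or after UDCA failure, and "The first date will be the one index date".
- Synopsis, exposure variable: "The exposure variable is the use of OCA initiated at the index date".
- Section 8.3: in Komodo Health, "OCA exposure will be assessed as date of first filled prescription"; in the registry, exposure runs from the first use that the physician reports.

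Section 10.1.1 also says that a patient can give at most one OCA-treated index "because prior treatment with OCA is an exclusion criterion".

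**The concern.** An inclusive look-back takes in the index day. For an OCA index, the index day is defined by OCA evidence. The rule that should keep out prevalent OCA users therefore also keeps out new users, who are the treatment group.

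The stake is that a core cohort rule cannot be run as written. Section 7.3 is one of the two criteria lists that Section 10.1.1 says are assessed at every decision point. Two groups work separately: Section 11 says that registry data may not leave the registry, and Section 12.6 provides separate SOPs for the Global PBC study group and for the CRO analysing Komodo. Each would have to repair the rule for itself, and more than one repair is possible. Section 10.11 requires deviations to be logged and all Investigators to agree to protocol changes. If the text stands, the first eligibility run therefore needs either a logged deviation or an undocumented departure.

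**Working it through.** **Step 1. Reproduce the plan's planning figures.** Inputs from Section 10.4: 395 OCA and 5916 control patients (Komodo), 344 and 2200 (Global PBC), HR 0.5, alpha 0.05, VIF 1.5 or 2.0, reference power 80%. Section 10.3.1 makes the test two-sided. Schoenfeld's formula with variance inflation is

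events = VIF × (1.96 + 0.8416)² / [p(1 − p) × (ln HR)²], with p = OCA/(OCA + control).

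- Komodo: p = 395/6311 = 0.0626 and p(1 − p) = 0.0587. Events at VIF 1 are 7.849/(0.0587 × 0.4805), or 279 after rounding up. Required event rate: 6.6% at VIF 1.5 and 8.8% at VIF 2.0. The plan says above 6% and above 9%.
- Global PBC: p = 344/2544 = 0.1352 and p(1 − p) = 0.1169. Events at VIF 1 are 7.849/(0.1169 × 0.4805), or 140 after rounding up. Required event rate: 8.2% and 11.0%. The plan says above 8% and above 11%.

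The thresholds reproduce, apart from loose rounding of the Komodo 6% (power there is 76.0%, and 82.2% at 7%). The plan's power rests on all 395 and 344 initiators being eligible.

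**Step 2. Apply the criterion literally.** Let D be the first date with evidence of OCA, and T the OCA index date.

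- Sections 7.1.1 and 7.4 set T at a date of OCA evidence, so D ≤ T.
- Section 7.3 with the inclusive boundary excludes the index whenever D ≤ T.
- That condition always holds. If D = T (a new user), the index day triggers the exclusion. If D < T (OCA use before the qualifying date), the earlier use triggers it.

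So 395 becomes 0 and 344 becomes 0. With p = 0, p(1 − p) = 0, and neither the weights nor the hazard ratio can be estimated.

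**Step 3. Apply the Section 10.1.1 reading.** Excluding only D < T keeps new users and removes prevalent users. The counts 395/5916 and 344/2200 stand, and so do the thresholds in Step 1.

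**Step 4. Check the control side.** A control index must not initiate OCA on its index date (Section 7.4). The inclusive OCA wording therefore does no harm there, and changing it to strictly before admits no additional control index.

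**The case against.** The strongest reply is that nobody could misread the intent. Section 7.4 refers the reader to Section 10.1.1 for the full method of group assignment, and that section limits the exclusion to prior treatment. Section 10.4 counts initiators who meet entry criteria. The inclusive tag is attached to most bullets in Section 7.3 and looks like boilerplate. Literal coding would give an empty arm, which would show in the last row of Tables 1A and 1B in Appendix B. Section 10.1.2 also requires Clean Room Committee approval of the datasets before event data are opened. All of this stands. It limits the practical risk, but it does not make the criterion executable.

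It could also be argued that a prescription may be dated before its fill, so that the index day need not carry OCA use. The synopsis closes this gap, since it defines exposure as use initiated at the index date.

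Three stronger readings are tempting, and the documents do not support them.

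- A reader might infer that the sponsor chose a design that excludes initiators. Sections 10.1.1 and 10.4 show the opposite.
- A reader might infer that 395 and 344 patients are lost. That is only the literal consequence. What fails is the OCA index; the same patients may still contribute control indices from before OCA initiation (Section 7.4).
- A reader might infer that the wording lets fibrate users in. As written it does not. That would need a careless repair that removes the inclusive boundary from the whole bullet. Even then, Section 6.1 censors at fibrate initiation, so a fibrate started on the index day would add essentially no follow-up.

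**Conclusion.** The criterion is wrong as written, and the documents themselves show it. It is an internal contradiction in an operative eligibility rule. The literal effect is no eligible OCA-treated index in either study. The expected effect on the analysis is nil provided that both teams apply the Section 10.1.1 reading. Planned sample size and power are unaffected.

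Two assumptions underlie this. First, OCA evidence on the index day counts as use on that day, as the synopsis and Section 8.3 indicate. Second, the 395 and 344 are taken as given. Section 6.2 describes them by diagnosis, UDCA failure and OCA initiation (Komodo) or by OCA initiation alone (registry) and does not list the Section 7.3 exclusions, so the documents do not show how many remain after the full set is applied. That uncertainty exists with or without this correction.

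**What to change.** In Section 7.3 and in the synopsis, split the bullet in two:

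- evidence of OCA use strictly before the index date, in line with Section 10.1.1;
- evidence of fenofibrate or bezafibrate use, with the existing inclusive boundary unchanged.

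Do not drop OCA from the list or exempt the OCA group. Section 7.4 takes the first OCA date at or after UDCA failure, so this exclusion is what removes a patient who used OCA before that date. The change concerns the cohort filter only. It needs no new data and no recalculation, and it costs one criterion reworded in two places. Made before the eligibility filter is run, it gives both teams the same rule and avoids a logged deviation on the cohort definition.

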7.4. Group Assignments

Treatment group (OCA-treated): ≥ 1 prescription or medical claim for OCA at or after UDCA failure date. The first date will be the one index date.

Control Group (Non-OCA-treated but eligible for OCA): Each date corresponding to evidence of a patient meeting the definition of UDCA inadequate response or intolerance in which the patient meets the inclusion and exclusion criteria and does not initiate OCA will be an

index date for the non–OCA-treated patient group. Patients may contribute indices to this group before they initiate OCA, but not after OCA index.

A thorough description of methodology underlying group assignment can be found in Section 10.1.1.

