As the probabilities used to construct the weights are not known, they will be estimated using a logistic regression model. The model will be fit using observed treatment as the outcome and main effect terms for each of the covariates. Covariates (assessed in the pre-index period) will include:

- Age at index date
- Sex
- Most recent liver biochemistry levels (TB, ALP, ALT, AST)
- Most recent platelet counts
- Time (in months) since UDCA failure
- Clinical evidence of portal hypertension (platelets <150,000 and/or non-bleeding varices)
- Cirrhosis
 - Komodo Health: cirrhosis diagnosis with liver imaging and/or biopsy within 6 months before diagnosis
 - Global PBC registry: biopsy stage 4, transient elastography ≥16.9 kPa, radiological evidence (nodular liver or enlargement of portal vein with splenomegaly), clinical features of portal hypertension defined as platelet count <140 000/mm³ with persistent decrease in serum albumin; or, TB >2x ULN, or prothrombin time/INR > ULN (not due to antithrombotic use)
- Most recent Charlson Comorbidity Index Score (Glasheen 2019)
- Insurance type at the index date (Komodo Health only: commercial, Medicare, Medicaid, dual eligible, other)

All diagnosis, procedure and laboratory codes used to define the control variables are listed in Appendix A.

Once the weights are constructed, a table of weighted SMDs between the groups will be constructed to assess balance. An absolute SMD of greater than 0.1 will indicate potentially problematic residual imbalance for the particular covariate. In the case that either the model-fitting algorithm fails to converge, or residual imbalance exists after weighting, the study team will attempt to reduce model complexity or reduce imbalances by implementing one or more of the following actions:

- Adding/removing interaction terms (1st order or higher)
- Using a spline for continuous variables
- Shrinking all coefficients in the model using a penalty

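### A control index needs an abnormal ALP or bilirubin on its date and an OCA index does not, so OCA initiators with currently normal values have almost no control support; the direction of any bias is open

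*Combined protocol and SAP*

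**What the plan says.** **Control index.** Section 7.4 creates one for "Each date corresponding to evidence of a patient meeting the definition of UDCA inadequate response or intolerance" on which the other criteria are met and OCA is not started. Section 10.1.1 agrees: "Each date of inadequate response identified in the data will be considered a treatment decision point, and that date will be considered an index date". Both routes to failure in Section 7.1.1 need an abnormal test. Inadequate response requires "At least 1 measure of ALP and/or TB >ULN; and" at least 270 days of prior UDCA. Intolerance is "A maximum of 90 days of UDCA use with ALP>ULN and/or TB >ULN".

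**OCA index.** Section 7.4 takes the first "prescription or medical claim for OCA at or after UDCA failure date". No test is required at or near that date, and Section 7.1.1 sets no limit on the age of the abnormal result. The plan expects a gap, because "Time (in months) since UDCA failure" is a propensity covariate in Section 10.1.1.

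**Weighting and checks.** Controls are reweighted to the OCA group's covariate distribution, using the latest TB, ALP, ALT and AST in the 12-month pre-index period. Section 10.1.1 invokes positivity and gives one numerical trigger: "An absolute SMD of greater than 0.1 will indicate potentially problematic residual imbalance for the particular covariate". Section 10.2 also puts baseline covariates in the weighted Cox model. Section 4.5.3 justifies the control group by saying that eligibility is standardised across treated and untreated patients.

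**The concern.** Take a patient who failed UDCA two years ago and whose latest ALP and TB are now normal. If OCA starts today, the patient enters the analysis. If it does not, today yields no record. Entry at that covariate value depends on treatment, which a target trial emulation is meant to prevent and which Section 4.5.3 says does not happen.

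The estimand makes this matter. SMR weighting asks what would have happened to the treated had they not been treated. For initiators with normal current values, the data hold essentially no untreated indices in the same position. Their counterfactual comes from a logistic model, and then a Cox model, fitted to controls with abnormal values. If risk changes shape near ULN, that extrapolation can move the hazard ratio in a study that tests HR = 1.

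**Working it through.** **1. The two entry rules side by side**

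| | Control index | OCA index |
|---|---|---|
| Trigger | Date with evidence of UDCA failure | First OCA prescription or claim |
| ALP and/or TB above ULN | On the date of evidence | Once, at any earlier time |
| Recency limit | Not needed | None |
| Latest ALP and TB both normal | Essentially excluded | Allowed |

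**2. What the plan could detect.** The 0.1 rule compares means. In a large-sample calculation with normal-value shares q of 5–20%, the weighted ALP SMD lay between −0.07 and +0.02. In a separate simulation the largest absolute value was 0.034. The trigger would not have fired in either. Appendix B plans range and quartile displays of TB and ALP (Table 19), weight distributions (Table 29) and propensity plots (Figures 3A and 3B). These might show the gap, but no trimming or common-support rule says what follows.

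**3. Size if risk steps down at ULN.** Assume risk is flat above ULN and that normal-value patients have k times that hazard. Under no drug effect the apparent ratio is 1 − q(1 − k):

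| q (assumed) | k = 1/3 | k = 1/2 |
|---|---|---|
| 5% | 1 − 0.05 × 0.667 = 0.967 | 0.975 |
| 10% | 0.933 | 0.950 |
| 20% | 0.867 | 0.900 |

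Because every control has the same hazard here, the weights cannot change the answer. The result is the step assumption restated.

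**4. Size under other risk shapes.** The simulation had a true ratio of 1, ALP only, six visits, latent SD 0.45 and visit noise 0.15–0.5 on log ALP (all assumed). Control indices arose only at abnormal visits, and OCA could start at any visit after first failure. About 5–21% of OCA indices had normal values.

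| Risk shape | SMR-weighted | With outcome covariates |
|---|---|---|
| Log-linear in ALP | 1.00–1.09 | 0.99–1.01 |
| Flat below ULN, rising above | 1.02–1.12 | 1.00–1.04 |
| Step up at ULN | 0.89–0.99 | 0.88–0.99 |
| Any shape, OCA indices limited to abnormal latest values | 0.98–1.02 | 0.98–1.02 |

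A second calculation, with gamma-distributed ALP and linear logistic SMR weights, gave for q = 5 / 10 / 20%:

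- hazard doubling per doubling of ALP: 0.99 / 1.06 / 1.11
- flat below ULN, rising above: 1.00 / 1.07 / 1.13
- halved just below ULN with a 1.5-fold slope above: 0.99 / 1.00 / 0.98

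**5. Power cost of restricting the OCA arm.** Inputs from Section 10.4 are 395 OCA and 5916 control patients (Komodo), 344 and 2200 (Global PBC), alpha 0.05, HR 0.5; Section 10.3.1 makes the test two-sided.

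Power = Φ(|ln HR| × √(D p(1 − p)/VIF) − 1.96), where D is the number of events and p the OCA share.

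*The plan's figures.* Taking the event rate as the control rate r and the OCA rate as 1 − (1 − r)^HR, 80% power is reached at 6.8% (Komodo) and 8.8% (Global PBC) for VIF 1.5, and at 9.1% and 11.8% for VIF 2.0. Cut to whole percents these are the stated 6, 8, 9 and 11.

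*The cost.* This applies one event rate to all patients.

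- Komodo, 6%, VIF 1.5: D = 0.06 × 6311 = 378.7; p(1 − p) = 0.0587; 0.693 × √(378.7 × 0.0587/1.5) − 1.96 = 0.708; power 76.0%.
- With 10% of OCA indices removed (355.5 left): D = 376.3; p(1 − p) = 0.0535; 0.693 × √(376.3 × 0.0535/1.5) − 1.96 = 0.579; power 71.9%.
- For 5, 20 and 30% removed, Komodo power is 74.0, 67.0 and 61.5%.
- Global PBC, 8%, VIF 1.5: 78.8%, falling to 75.1% with 10% removed.

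**The case against.** A reader might infer that normalised initiators are low risk, so the comparison must favour OCA. The documents do not support that. They describe inadequate responders as being at higher risk and ALP as a surrogate for outcome, but give no risk function around ULN. The inference needs a step at ULN. With a gradient above ULN the ratio mostly stayed near 1 or moved against OCA, and the Cox covariates of Section 10.2 removed most of that movement. They did not remove the bias in the step case.

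A reader might also infer that such initiators can have no control at all. That is too absolute. Section 12.4.4 gives an ALP ULN of 121 at LabCorp (age 21 or over) against 153 at Quest for women aged 50 or over, so a raw value of 122–153 is abnormal at one and normal at the other. That overlap reflects units rather than clinical comparability, but the plan does not say which scale enters the model. Nor does it say whether an intolerance index falls on the laboratory date or the UDCA stop date, or whether the index-day result counts as the latest value. If it does not, some controls would have normal covariate values.

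The affected share may be small: OCA is labelled for inadequate UDCA response or intolerance, and at q = 5% even the step case gives about 0.97. The Clean Room Committee (Section 10.11) can change inclusion criteria and variable definitions, and Section 10.1.1 allows splines and interactions. These points limit the likely size and leave room for repair. They do not close the gap, because a more flexible model still has almost no controls there and nothing obliges the Committee to act.

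Section 7.2 assesses criteria at each index date, which could be read as requiring current abnormality. It refers back to a definition without recency, so if that is the intent the text must say so.

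**Conclusion.** The asymmetry between arms is in the text and produces a structural positivity gap for an effect-in-the-treated estimand. It also conflicts with the rationale in Section 4.5.3. The size is unknown because the share of OCA initiators with normal latest ALP and TB is not reported. For assumed shares of about 5–20%, the null ratio ranged from about 0.87 to 1.13 across risk shapes, so neither sign nor magnitude can be claimed. Those figures rest on assumed ALP distributions and risk functions and ignore TB. The entry-rule comparison does not depend on them.

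**What to change.** In Sections 7.1.1 and 7.4, apply one index-date biochemical criterion to both arms: the ALP and TB results closest to the OCA index, on or before it and within the look-back used for controls, must include at least one above ULN. State whether the index-day result counts, which date anchors an intolerance index, and whether ALP enters the model as a multiple of ULN.

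Before outcomes are released under Section 10.1.2, report by data source the number of OCA indices with normal latest ALP and TB. Show the unrestricted cohort as a sensitivity analysis.

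The work is a wording change and one filter on data already held. The costs are the loss of some OCA indices from the primary analysis, with the power loss shown above on counts that precede the LabCorp linkage, and a narrower estimand: the effect in initiators with current biochemical abnormality.
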